Study Protocol and Statistical Analysis Plan

Official Title:

The Effect of the Flipped Classroom Model on Nursing Students' Pediatric Pain Management Knowledge and Learning Motivation: A Randomized Controlled Trial (FLIPNURSE)

Unique Protocol ID:

ErsoyU-[name]-FC2022

NCT Number:

Pending (to be assigned)

Sponsor/Collaborators:

Faculty of Health Sciences, Burdur Mehmet Akif Ersoy University

Principal Investigator:

[name], Assistant Professor

Version/Date:

Version 1.0 — August 31, 2021

The Effect of the Flipped Classroom Model on Nursing Students' Pediatric Pain Management Knowledge and Learning Motivation: A Randomized Controlled Trial Abstract

Aim

The aim of this study is to evaluate the effect of the flipped classroom model on nursing students' knowledge level and learning motivation in pediatric pain management.

Background

Pain management in children is an important and multidimensional responsibility in nursing. However, the time allocated to pediatric pain and the opportunities for practical application in nursing education programs are limited. The integration of active learning approaches is necessary to increase knowledge and motivation in this area.

Design

This study is a parallel-group, randomized controlled experimental study conducted at a state university in Turkey.

Methods

A total of 84 third-year nursing students were randomly assigned to an intervention (n=42) and control (n=42) group. The intervention group was taught using the flipped classroom model, while the control group was taught using the self-directed learning model. Data were collected at three time points (pre-test, post-test, and 3 months post-intervention) and analyzed using a two-way mixed-design ANOVA.

Results

At baseline, there were no significant differences between the groups in terms of knowledge and motivation levels (p > 0.05). After the training, significant and sustainable increases were observed in both variables in the intervention group (p < 0.001), while no significant changes were observed in the control group.

The group × time interaction was found to be significant for both variables, indicating that the flipped classroom model provides an effective and sustainable contribution to knowledge level and motivation.

Conclusions

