2.3. Sample, randomization, and prevention of bias

The population of this study consisted of a total of 152 third-year nursing students enrolled in the Child Health and Nursing course. Sample size and power analysis were performed using the G*Power 3.1.9 program. Considering the research design (three measurements and two groups), the following parameters were used for the ANOVA test in repeated measurements: $\alpha = 0.05$, power $(1-\beta) = 0.80$, and moderate effect size (f = 0.25). Accordingly, a minimum of 27 participants per group and a total of at least 54 participants were required. Considering potential data losses, the study was conducted with 44 participants in each group (Cohen, 2013; Faul et al., 2009).

Students were divided into two groups using stratified sampling based on their academic achievement levels. Those with an academic grade point average between 2.00 and 3.00 formed the first stratum, while those with a grade point average between 3.01 and 4.00 formed the second stratum. Within each stratum, participants were assigned to either the intervention or control group in equal numbers using a computer-assisted simple random assignment method with blind allocation. The randomization process was conducted by an independent biostatistician not involved in the study, and no blocking randomization or other restriction methods were used.

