2.10. Data analysis

Data analysis was performed using IBM SPSS 25.0 (IBM Corp., Armonk, NY, USA). The assumption of normal distribution was evaluated using the Kolmogorov–Smirnov test and supported by skewness and kurtosis values within the ± 2 range. The internal consistency of the scales was determined using Cronbach's alpha coefficient.

Within the scope of statistical analysis, frequency distributions and descriptive statistics were calculated; independent samples t-test and chi-square test were used for intergroup comparisons. Two-Way Mixed ANOVA was applied to examine the effects of group, time, and group × time interaction on education. All necessary assumptions (e.g., normal distribution,

variance homogeneity, sphericity) were tested and found to be met in this analysis. The significance level was set at p<0.005 for all statistical analyses. Additionally, no subgroup analyses were conducted for variables such as age, gender, or academic achievement. All analyses were designed to focus on between-group comparisons.

3. Results

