3.1. Intergroup Comparison of Descriptive Characteristics of Students

The descriptive characteristics of students in the intervention and control groups (n=84) are presented in Table 1. No significant differences were found between the groups in terms of age, gender, academic grade point average, and pain management self-assessment scores (p>0.05).

Table 1. Descriptive Characteristics of Students

Descriptive Characteristics	Intervention Group \(\overline{X} \pm SS \\ (Min - Max)		Control Group $\overline{X}\pm SS$ (Min – Max)		t	p
Age		9 ± 2.32 0–31)	21.86 ± 1.64 $(20-29)$		0.757	0.125
Pain management self- assessment (0-10 points)	4.52 ± 1.19 (2-7)		4.33 ± 1.05 (2-6)		0.776	0.333
Gender	n	%	n	%	Chi- square	p
Female	31	73.8	27	64.3	0.345	0.891
Male	11	26.2	15	35.7	0.343	
Academic grade point average						
2.00–3.00	21	50	21	50.0	0.001	1.00
3.01–4.00	21	50.0	21	50	0.001	
t: Independent samples t-test, chi-squa	are test					

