3.2. Findings Related to the Level of Knowledge About Pediatric Pain Management

According to the pre-test results, there was no significant difference between the intervention group and the control group in terms of pediatric pain management knowledge level (p > 0.05). However, according to the two-way mixed design ANOVA analysis, group effect (F=16.789, p < 0.001, η^2 =0.170), time effect (F=23.251, p<0.001, η^2 =0.221), and group*time interaction (F=27.834, p<0.001, η^2 =0.253) were found to be statistically significant. In particular, the significance of the group*time interaction indicates that the two groups showed different patterns of change in their knowledge levels over time (Table 2).

In the intervention group, a significant increase was observed in students' pediatric pain management knowledge scores. The mean score, which was 78.04 ± 18.79 in the pre-test, increased to 105.92 ± 23.62 in the post-test and was recorded as 92.26 ± 23.40 in the retention

test. The use of different letters (a, b, c) to denote the means obtained at different measurement times indicates statistically significant differences over time. However, in the control group that received education using the self-learning model, the knowledge level scores remained quite close to each other over time, and no significant change was detected (pre-test: 79.33±19.19, post-test: 78.09±14.68, retention test: 77.16±15.94). These findings indicate that the flipped classroom model is more effective than the self-directed learning model in improving knowledge levels in pediatric pain management and ensuring the retention of this knowledge (Figure 1).

Table 2. Pediatric Pain Management Knowledge Level Scores of the Intervention and Control Groups

Pediatric Pain Management	Intervention group (n=44)	Control group (n=44)	Statistic	Group	Time	Group*time interaction	
Knowledge Scale	Mean (SD)	Mean (SD)	Statistic				
Pre-test	78.04 (18.79) ^a	79.33 (19.19) ^a	F	16,789	23,251	27,834	
Post-test (4th week)	105.92 (23.62) ^b	78.09 (14.68) ^a	p	<0.001	<0.001	<0.001	
Retention Test (3rd month)	92.26 (23.40)°	77.16 (15.94) ^a	η^2	0.170	0.221	0.253	

a-c: Different letters indicate statistically significant groups within each column.

F: two-way mixed design analysis of variance; η^2 , partial eta square; SD, standard deviation.

[figure not shown]

Figure 1. Mean Scores of Pediatric Pain Knowledge by Group and Time

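### Two significance thresholds are stated: section 2.3 sizes the trial at alpha 0.05, while section 2.10 applies 0.005 to every analysis without giving a reason

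*Combined protocol and SAP*

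**What the plan says.** Section 2.3 bases the sample size on a repeated-measures ANOVA with two groups and three measurements, alpha 0.05, power 0.80 and f = 0.25. It concludes that "a minimum of 27 participants per group and a total of at least 54 participants were required". It names neither the ANOVA term being powered nor the correlation assumed between visits. It then says: "Considering potential data losses, the study was conducted with 44 participants in each group". The Abstract gives a different total: "A total of 84 third-year nursing students were randomly assigned to an intervention (n=42) and control (n=42) group".

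Section 2.10 sets the decision rule: "The significance level was set at p<0.005 for all statistical analyses". It mentions no multiplicity adjustment and offers no other reason for this level.

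The results describe baseline non-significance as p above 0.05 in four places: the Abstract and sections 3.1, 3.2 and 3.3. Tables 2 and 3 report all six ANOVA effects as p below 0.001.

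**The concern.** The two thresholds differ tenfold. Because section 2.10 covers every analysis, 0.005 cannot be read as a rule for secondary or post-hoc tests only. Section 2.1 says the analysis methods stayed the same throughout, so no documented change of plan explains the difference.

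Two things are at stake. The threshold is the rule by which both hypotheses are judged, and the reader is given two. The stated 80% power also belongs to the looser threshold, so if 0.005 is the real rule, the power statement describes a test that was not the one applied.

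**Working it through.** **Step 1. Does 54 reproduce at 0.05?**

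Inputs from section 2.3: f = 0.25, m = 3 visits, 2 groups, equal allocation, alpha 0.05, power 0.80. Assumed, because the document does not give them: the tested effect, the between-visit correlation ρ, and sphericity. Power comes from the noncentral F distribution:

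- Interaction: λ = N·f²·m/(1 − ρ), with 2 and 2(N − 2) degrees of freedom.
- Group effect: λ = N·f²·m/(1 + 2ρ), with 1 and N − 2 degrees of freedom.

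At N = 54, N·f²·m = 54 × 0.0625 × 3 = 10.125.

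- Interaction, ρ = 0: λ = 10.125, critical F(2, 104) = 3.08, power 0.809. At N = 52 power is 0.792, so 54 is the smallest even total.
- Group, ρ = 0.10: λ = 10.125/1.20 = 8.44, critical F(1, 52) = 4.03, power 0.81.
- Group, ρ = 0.12: λ = 10.125/1.24 = 8.17, power 0.80.

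So the 54 is sound at 0.05 under these inputs. Other correlations do not return it. For example, ρ = 0.5 gives 28 (interaction) or 86 (group).

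**Step 2. Change only alpha, to 0.005.**

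At N = 54 the critical values rise to 5.58 (interaction) and 8.60 (group).

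| Assumed inputs | N = 54: power at 0.05 / 0.005 | N = 84: power at 0.05 / 0.005 | N = 88: power at 0.05 / 0.005 | Smallest even N for 80% at 0.005 |
|---|---|---|---|---|
| Interaction, ρ = 0 | 0.81 / 0.50 | 0.95 / 0.79 | 0.96 / 0.81 | 88 |
| Group, ρ = 0.10 | 0.81 / 0.50 | 0.95 / 0.77 | 0.96 / 0.79 | 90 |
| Group, ρ = 0.12 | 0.80 / 0.48 | 0.94 / 0.75 | 0.95 / 0.78 | 94 |

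One row needs exactly 88, the total implied by 44 per group. That is not evidence that 0.005 was planned, because section 2.3 attributes the larger number to expected data losses.

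**Step 3. Does any reported result depend on the choice?**

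The six reported F values, with 84 participants, give p from about 1 × 10⁻⁴ (knowledge, group effect) to about 1 × 10⁻²² (motivation, interaction). All pass either threshold. The Table 1 p-values are 0.125 or larger and fail both. No reported p-value falls between 0.005 and 0.05.

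The lettered within-group contrasts carry no p-values. The closest one is knowledge in the intervention group, post-test against retention: 105.92 − 92.26 = 13.66, SDs 23.62 and 23.40. I take n = 42 because the reported partial eta squared values match 84 participants, not 88. The correlation can be inferred from the knowledge results, assuming compound symmetry:

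- The group means over the three visits are 92.07 and 78.19, each 6.94 from the overall mean. The group sum of squares is 3 × 42 × 2 × 6.94² = 12,137. Dividing by F = 16.789 gives a between-subject mean square of 722.9.
- The interaction sum of squares from the six cell means is 8,951 on 2 degrees of freedom. Dividing 4,475 by F = 27.834 gives a within-subject mean square of 160.8.
- ρ = (722.9 − 160.8)/(722.9 + 2 × 160.8) = 0.54.
- The average variance from the Table 2 SDs is 382.7. It gives ρ = (722.9/382.7 − 1)/2 = 0.44, or ρ = 1 − 160.8/382.7 = 0.58.

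At ρ = 0.44 the SD of the difference is √(23.62² + 23.40² − 2 × 0.44 × 23.62 × 23.40) = 24.9, so t = 13.66/(24.9/√42) = 3.56 and the unadjusted p is 0.00096. At 0.54 it is 0.0003, and at 0.58 it is 0.0002. The p-value reaches 0.005 only if ρ falls to about 0.19.

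**The case against.** The strongest objection is to the power figures. Section 2.3 gives no correlation, and the table uses only values that return 54 at 0.05. With ρ = 0.4, the interaction test needs exactly 54 at 0.005. The trial's own knowledge data suggest ρ of 0.44 to 0.58. There the interaction test has power 0.85 to 0.95 at 54 under 0.005, and at least 0.98 at 84. The group test at those correlations has only 0.57 to 0.62 at 54 even under 0.05, so its shortfall is not due to the threshold alone. Over ρ from 0 to 0.7, the total needed at 0.005 runs from 88 down to 28 for the interaction and from 76 up to 176 for the group effect.

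This stands as a limit on the size: the power loss is conditional on the inputs. It does not remove the point. Section 2.3 says its 54 was computed at 0.05, where ρ = 0.4 gives 34. The conflict between the two stated thresholds also needs no power calculation.

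It can also be said that 0.005 is plainly a slip for 0.05, that 84 or 88 students were studied rather than 54, and that no finding changes. A slip is plausible given the repeated p above 0.05 wording, but that wording cannot prove it, since any p above 0.05 is also above 0.005. The other two observations are correct and keep the point minor.

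**Conclusion.** The inconsistency is real and rests on two explicit statements, with no assumption needed: alpha is 0.05 for sizing and 0.005 for analysis, unexplained. Its consequence for power does rest on assumptions. Under the inputs that reproduce 54, the stated 80% does not hold at 0.005; the shortfall is large at 54 and small at the 84 analysed.

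The reported conclusions are unaffected. The main ANOVA results clear either threshold without any assumption about ρ. For the closest lettered contrast, that judgement applies a pooled correlation to one arm and one pair of visits, and uses an unadjusted test. Minor, with high confidence.

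**What to change.** State the same threshold in sections 2.3 and 2.10.

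- If 0.005 is a slip, change section 2.10 to 0.05. Nothing else on this point needs to change.
- If 0.005 was intended, give the reason and restate the power at 0.005 for 54 and for 84, naming the tested effect and the assumed correlation.

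The cost is a wording correction, plus one restated power calculation if 0.005 is kept. It needs no additional participants and no reanalysis.

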However, a review of the literature reveals that no randomized controlled trial has yet been conducted to evaluate the effectiveness of the flipped classroom model in the field of pediatric pain management. Current systematic reviews and meta-analyses clearly emphasize that randomized controlled studies on the reverse class approach have primarily focused on general nursing practices or general pediatrics topics; no direct randomized controlled study specifically addressing pediatric pain management has been identified. (Barranquero-Herbosa, Abajas-Bustillo, & Drtego-Maté, 2022; Shi et al., 2025). This gap in the literature highlights the need for empirical studies evaluating the impact of pedagogical innovations in nursing education. This study aims to address this need by examining the effect of the flipped classroom model on nursing students' knowledge level and learning motivation in pediatric pain management.

Research Hypotheses

Hypothesis 1: The pediatric pain knowledge scores of students educated with the flipped classroom model are significantly higher than those of the control group.

Hypothesis 2: The learning motivation scores of students educated with the flipped classroom model are significantly higher than those of the control group.

2. Methods

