4.1. The Effect of the Flipped Classroom Model on Pediatric Pain Knowledge Level

A statistically significant and sustained increase in the knowledge levels of nursing students regarding pediatric pain management was observed in those who received education through the flipped classroom model. In particular, the high scores in the retention test compared to the pre-test level indicate the sustainability of learning in the long term. This can be attributed to the flipped classroom model's structure, which encourages active student participation, and its provision of application-based learning environments (Liu et al., 2018; Xu et al., 2019).

These results are consistent with the existing literature. The flipped classroom approach has been shown to enhance knowledge levels in nursing and medical education through various studies (Betihavas et al., 2016; Barranquero-Herbosa, Abajas-Bustillo, & Ortego-Maté, 2022; Merrou et al., 2023). Especially in clinical and applied fields, this model, supported by case analyses, problem-based learning, and group discussions, is reported to enable students not only to acquire knowledge but also to develop their abilities to analyze, evaluate, and transfer knowledge (Liu et al., 2018; Xu et al., 2019; Merrou et al., 2023; Alshehri, Levett-Jones, & Pich, 2024).

The learning gains in question are not limited to quantitative increases in knowledge but also reflect cognitive depth. In this context, the findings can also be evaluated within the framework of Bloom's cognitive domain taxonomy. The flipped classroom model contributes to the activation of higher-order cognitive processes such as analysis, synthesis, and evaluation

beyond the levels of knowledge and comprehension (). Similarly, in a study by Paralikar et al. (2022), it was noted that students who participated in the flipped classroom model showed significant development in Bloom's higher cognitive levels and achieved success, particularly in the application and analysis levels. It is stated that this model facilitates students' access to basic knowledge through offline preparation and reinforces their knowledge with higher-order thinking skills in an interactive classroom environment (Paralikar et al., 2022).

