In addition to these comprehensive cognitive contributions, the uniqueness of the study area is also noteworthy. The limited number of studies evaluating the effectiveness of the flipped classroom model in narrow and clinically critical areas such as pediatric pain management using a randomized controlled design increases the contribution of the findings to the literature.

The findings indicate that the flipped classroom approach is more effective than the traditional self-learning model in terms of increasing and maintaining knowledge levels in both the short and long term. This result shows that active classroom interaction and practical work carried out after the pre-learning process contribute positively to the retention of learning. Indeed, studies conducted by Sáiz-Manzanares et al. (2020) also emphasize that learning environments with high levels of active participation have a significant impact on knowledge retention (Sáiz-Manzanares et al., 2020).

However, some limitations of this model have also been noted in the literature. In particular, it has been pointed out that factors such as difficulty in accessing digital materials and insufficient assumption of individual learning responsibility may negatively affect student motivation (Busebai & John, 2021). However, in this study, maintaining a strong technical infrastructure and ensuring high accessibility of the digital platform used minimized such negative effects and supported the effectiveness of the learning process.

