4.2. The Effect of the Flipped Classroom Model on Learning Motivation

Statistically significant increases in the motivation levels of students who received education through the flipped classroom model were recorded in both the short and long term. In contrast, no significant change in motivation scores was observed in the control group where the self-directed learning model was applied. These findings indicate that the flipped classroom approach is effective in increasing students' interest in the material, encouraging active participation in class, and supporting intrinsic motivation.

In the literature, the positive effect of the flipped classroom model on learning motivation is supported by various studies. According to systematic reviews and meta-analyses conducted by Betihavas et al. (2016) and Liu et al. (2018), flipped classroom models have been found to have significant positive effects on learning motivation, autonomy, and self-efficacy (). In particular,

applications supported by case-based and problem-focused learning methods are noted to more effectively engage students in the learning process and enhance motivation (Merrou et al., 2023).

However, studies also highlight that this positive effect on motivation is not always sustainable. Some findings have revealed that the flipped classroom model creates high motivation among students in the initial stage, but motivation decreases over time when digital content is presented in an uninteractive, repetitive, or inadequate manner (Lo & Emp; Hew, 2019; Betihavas et al., 2016). This situation demonstrates that not only the structure of the learning model but also the quality of the content presented and the level of interaction are decisive factors in the sustainability of motivation.

Among the key factors that enable motivation to be sustained in the long term are the timeliness of content, diversity of applications, active participation of students in the learning process, and quality of interaction with instructors (Chen et al., 2014; Martin et al., 2020). Indeed, in this study, the fact that motivation scores remained high even in the retention test compared to the initial level suggests that the pedagogical quality of the content design and the intensity of interaction in the learning environment played a supportive role in motivation.

5. Nursing Education Implications

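### The retention claims compare the groups, but no between-group difference with a confidence interval is reported at post-test or at 3 months

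*Combined protocol and SAP*

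**What the plan says.** Under Research Hypotheses, Hypothesis 1 reads "The pediatric pain knowledge scores of students educated with the flipped classroom model are significantly higher than those of the control group". Hypothesis 2 makes the same comparison for motivation. Neither names a visit.

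Section 2.10 gives the main analysis: "Two-Way Mixed ANOVA was applied to examine the effects of group, time, and group × time interaction on education". It adds that "All analyses were designed to focus on between-group comparisons". It names no contrast at a given visit, no post hoc method and no confidence interval.

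Sections 3.2 and 3.3 (Tables 2 and 3) report means (SD) per arm and visit, and F, p and partial eta-squared for group, time and interaction. They also report letters, explained by the footnote "Different letters indicate statistically significant groups within each column". Each column is one arm, so the letters compare visits within that arm. The only between-group comparisons at a single visit are at baseline.

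The retention conclusions are worded between groups. Section 3.2 calls the flipped classroom "more effective than the self-directed learning model in improving knowledge levels in pediatric pain management and ensuring the retention of this knowledge", and Section 4.1 claims superiority "in terms of increasing and maintaining knowledge levels in both the short and long term". The supporting argument in the Discussion is mostly within-arm: "the high scores in the retention test compared to the pre-test level indicate the sustainability of learning in the long term" (4.1) and "motivation scores remained high even in the retention test compared to the initial level" (4.2). The Abstract instead links sustainability to the significant group × time interaction.

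**The concern.** A claim that one teaching model retains knowledge better than another rests on the between-group difference at the retention visit. That difference is not reported, and neither reported between-group test supplies it:

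- The group main effect averages over all three visits, including the pre-test, where no training effect can exist.
- The interaction has 2 degrees of freedom. It shows that the two profiles differ, but not at which visit or by how much. A significant interaction is compatible with full, partial or no retention.

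The pre-test score and the grade-point (GPA) stratum used in randomization are not covariates in the analysis.

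At stake is what a reader takes from the claims of sustained and maintained knowledge. The printed means suggest that the knowledge advantage shrinks considerably between the two post-training visits. No between-group estimate, and no measure of its precision, tells the reader by how much.

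**Working it through.** **1. Which n fits.** Partial eta-squared = F·df1/(F·df1 + df2). With 42 per arm the error df are 82 and 164. Knowledge: group 16.789/(16.789 + 82) = 0.170; time 46.502/(46.502 + 164) = 0.221; interaction 55.668/(55.668 + 164) = 0.253. All match Table 2. With 44 per arm, the number in the table header, the group value would be 0.163. The check therefore uses 42, as in the Abstract.

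**2. Between-group differences** (intervention minus control, Tables 2 and 3), with SE = √[(SD₁² + SD₂²)/42] and Welch df:

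| Outcome, visit | Difference | SE | 95% CI |
|---|---|---|---|
| Knowledge, pre-test | 78.04 − 79.33 = −1.29 | 4.14 | −9.5 to 7.0 |
| Knowledge, post-test | 105.92 − 78.09 = 27.83 | 4.29 | 19.3 to 36.4 |
| Knowledge, 3 months | 92.26 − 77.16 = 15.10 | 4.37 | 6.4 to 23.8 |
| Motivation, 3 months | 101.50 − 85.61 = 15.89 | 2.69 | 10.5 to 21.2 |

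For knowledge at 3 months p = 0.0009, below both the 0.05 of Section 2.3 and the 0.005 of Section 2.10. With 44 per arm the two post-training knowledge intervals are 19.5 to 36.2 and 6.6 to 23.6.

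**3. What the group main effect measures.** Knowledge: (−1.29 + 27.83 + 15.10)/3 = 13.88. Over the two post-training visits alone: (27.83 + 15.10)/2 = 21.47.

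**4. Correlation between visits.** The interaction sum of squares is 21 × Σ(d − 13.88)² = 8,950.6, where d runs over the three knowledge differences. The within-subject mean square is (8,950.6/2)/27.834 = 160.8. The mean within-cell variance is 383 from the printed SDs, or 348 as implied by the F values. The average correlation is 1 − 160.8/383 = 0.58, or 1 − 160.8/348 = 0.54. It is an average over visit pairs, not the post-test to 3-month value itself.

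**5. Share retained, knowledge.** 15.10/27.83 = 0.54. The Fieller 95% interval (82 df) is 27% to 82% at a correlation of 0.54 and 27% to 81% at 0.58. The decline is 27.83 − 15.10 = 12.73 points (95% CI 4.5 to 21.0, or 4.8 to 20.6). No share is given for motivation, because its post-test mean of 120.66 exceeds the scale maximum of 120 in Section 2.2.3.

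**6. Do the inputs agree?** The within-cell sum of squares from the SDs is 41 × (sum of the six variances) = 94,151 for knowledge. From the F values it is 82 × 12,137.2/16.789 + 164 × 160.8 ≈ 59,280 + 26,369 = 85,649. For motivation the two figures are 42,824 and 49,498. If the whole gap lay in the 3-month cells, the 3-month intervals would be 7.6 to 22.6 (knowledge) and 9.3 to 22.5 (motivation). The direction holds either way.

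**7. Effect of baseline adjustment.** With an assumed pre/post correlation of 0.3 to 0.6 and a slope about equal to it, the 3-month knowledge difference becomes 15.10 + 0.3 × 1.29 = 15.5 to 15.10 + 0.6 × 1.29 = 15.9. The SE falls by 1 − √(1 − r²), or 5% to 20%.

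**The case against.** The case on the other side is substantial. The interaction compares the groups directly, and the Abstract uses it to support sustainability. The 2.10 sentence on between-group focus follows a statement that no subgroup analyses were done, so it can be read as meaning whole groups rather than subgroups. The hypotheses name no visit. The fall in scores is printed in text and tables, the letters mark it as significant, and Sections 4.1 and 4.2 state openly that the comparator is the starting level. Because the control arm is flat, the within-arm and between-group accounts are close at 3 months: 14.22 (92.26 − 78.04) against 15.10 for knowledge, and 17.89 (101.50 − 83.61) against 15.89 for motivation. GPA is exactly balanced (21 and 21 in each arm), and adjustment moves the knowledge estimate little.

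All of that stands, and it rules out several readings that a reader might infer. The documents do not support saying that between-group testing is absent, that the ANOVA is invalid, that sustainability is argued only within the arm, or that Section 2.10 promised a contrast and broke the promise. Nor do they support saying that the 3-month advantage would vanish.

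The objection does not supply a visit-specific difference with its precision. A reader can subtract the means, but the adjusted difference and the interval for the decline need individual data, and the printed inputs conflict.

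**Conclusion.** The point holds as a gap in estimation and reporting. The contrast behind the retention conclusions is the 3-month between-group difference, and it is reported neither with an interval nor adjusted for baseline. On the printed figures it is 15.10 points for knowledge and 15.89 for motivation, both clearly above zero. For knowledge that is about 54% of the post-test difference, with an interval of roughly 27% to 82%.

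These figures are provisional. They assume 42 per arm, complete data, no adjustment and SDs correct as printed. The retained share also treats the average correlation as that between the two post-training visits. A reader might take it as established that half of the advantage is lost; the width of the interval and the unreconciled inputs do not allow that. Direction and significance are not expected to change. The authors should make the change, but it does not overturn the trial's conclusion.

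**What to change.** 1. Reconcile four items against the raw data: n per arm (42 in the Abstract and Table 1, 44 in Section 2.3 and the headers of Tables 2 and 3); the SDs with the F values; the motivation mean of 120.66 with the maximum of 120; and the post-test timing (one month after training in Section 2.8, 4th week in Tables 2 and 3).
2. Keep the mixed ANOVA as reported. Add, labelled post hoc, a repeated-measures model of the post-test and 3-month scores with group, visit, group × visit, pre-test score and GPA stratum. Allow group-specific variances, since the post-test knowledge SDs are 23.62 and 14.68.
3. For each outcome, report the adjusted between-group difference with 95% CI at both visits, and the group × visit term as the decline.
4. Base the retention wording in the Abstract and Sections 3.2, 4.1 and 4.2 on the 3-month between-group difference. State the retained share and its interval as the reconciled rerun gives them; do not fix on about half in advance.

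The cost is a data check, one rerun on data already held, and one table row per outcome and visit. The drawback is that the results are known and Section 2.1 says the analysis methods did not change. Hence the post hoc label and the need to show both visits.
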